PANOBINOSTAT and RUXOLITINIB In MyElofibrosis

PRIME STUDY

Phase I/II Study of Combination oral JAK2 tyrosine kinase inhibitor (JAK2-TKI) and Histone Deacetylase Inhibitor (HDACI) therapy in patients with Myelofibrosis

PI: [name]

NCT01693601

Document Date: May 19, 2015

Mount Sinai School of Medicine

PANOBINOSTAT and RUXOLITINIB In MyElofibrosis

PRIME STUDY

Phase I/II Study of Combination oral JAK2 tyrosine kinase inhibitor (JAK2-TKI) and Histone Deacetylase Inhibitor (HDACI) therapy in patients with Myelofibrosis

Principal Investigator:

[name]
Mount Sinai School of Medicine
Tisch Cancer Institute
[name],
[name]
[name]
[contact]
[contact]

Co-Investigator [name] Mount Sinai School of Medicine Tisch Cancer Institute [name] [contact] [contact]	Co-Investigator [name] Mount Sinai School of Medicine Tisch Cancer Institute [name] [contact] [contact]	Co-Investigator/Statistician: [name] [name] [contact] [name]
---	--	--

Summary

This is a single-center, single arm, dose finding study to assess safety and tolerability of the oral combination of PANOBINOSTAT and RUXOLITINIB in patients with myelofibrosis (MF) in chronic and accelerated phase.

Study phase: I/II

Study objectives:

- Primary
 - Assess the safety and tolerability of RUXOLITINIB in combination with PANOBINOSTAT in patients with MF
 - Identify a recommended phase II dose of each agent in combination
 - Assess treatment response as defined by the International Working Group for Myelofibrosis Research and Treatment (IWG-MRT)
- Secondary
 - Assess changes in spleen size with combination therapy
 - Assess symptom response with a validated MPN tool
- Exploratory
 - Evaluate changes in biomarkers in relation to response to combination treatment with RUXOLITINIB and PANOBINOSTAT
 - Bone marrow histopathology
 - Cytogenetics
 - Acetylation of H2B and H3 histones
 - JAK2V617F peripheral blood mononuclear cell mutational load
 - Peripheral blood CD34+ hematopoietic cell load
 - Peripheral blood CD34+ hematopoietic cells expression of CXCR4
 - Peripheral blood cytokine profile
 - Evaluate a panel of biomarkers as predictors of response and prognosis
 - ASXL1, EZH2, TET2, and others to be determined

Study population:

Adult male or female patients ages 18 or older, who have been diagnosed with intermediate-2 or higher (IWG risk group) chronic and accelerated phase PMF, Post PV MF, or Post ET MF as defined by the World Health Organization. Only patients seen in the Mount Sinai Myeloproliferative Disease Program (MPD) clinic will be enrolled in this protocol. These patients will either be primary patients of this clinic or patients referred by outside hematologists or oncologists. Written informed consent must be obtained prior to any screening procedures. Patients may have received prior therapy for MF, however they must be

willing and able to discontinue all drugs used to treat underlying MF disease, at least 28 days or 5 half-lives (whichever is longer) prior to starting study drug. This trial will allow patients who were treated with either HDACis or JAK2is, as long as these agents were not discontinued due to clinically relevant toxicities as per the investigator's assessment.

Number of patients: 33 to 58

Overview of study design:

Phase I/II open label, single institution, combination therapy trial of induction RUXOLITINIB followed by combination with PANOBINOSTAT in dose escalation cohorts with a primary endpoint of determining the safety and tolerability of combination therapy in patients with myelofibrosis (MF) in chronic and accelerated phase. A 3+3 standard dose escalation scheme will be employed and the occurrence of dose limiting toxicities (DLTs) will be captured and the occurrence of such events will determine dose cohort escalation by predetermined and established rules. In addition to establishing the DLTs, maximally tolerated dose (MTD), and recommended phase II dose (RPTD) in the phase I portion of this trial, exploratory biomarkers will be evaluated within phase I as well. Pharmacodynamics and exploratory genetic and epigenetic biomarkers will be explored as predictors of response to therapy. The RPTD cohort will be expanded to incorporate a total of 22 patients, including 6 from phase I, in order to assess clinical response as assessed by International Working Group for Myelofibrosis Research and Treatment (IWG-MRT) as a primary endpoint for the phase II portion of this trial.

Screening for this study will have a window of 56 days and start on day -84 with signing of informed consent. See Figure 4-1 A and B. Eligible patients will begin induction phase therapy on day -28, receiving single agent RUXOLITINIB PO BID daily for 28 days. Patients who maintain a platelet count $\geq 50,000/\mu\text{l}$ at Day 1 will then receive concomitant PANOBINOSTAT PO TIW QOW or PO TIW QW depending on the cohort assignment.

The first 28 days of combination therapy will be the evaluable phase I portion of the study. Patients who do not experience a defined DLT in the evaluable phase I period can remain on study receiving combination drug therapy for a total of 6 cycles (cycles 2-6). See Figure 4-1 A. AEs will continue to be recorded on all patients (phase I and II) receiving combination therapy beyond the first cycle of the study. Dose escalation rules are based on the standard 3+3 design as shown in Figure 4-2.

Phase I patients who complete a total of 6 cycles of combination therapy will be assessed for clinical response by IWG-MRT criteria. Patients who achieve at least Stable Disease (SD) by IWG-MRT (Table 4-2) can remain on therapy indefinitely or until disease progression or drug toxicity as assessed by the investigators. At the discretion of the investigator, phase I patients who have completed 6 cycles of therapy with a minimum of SD can also be dose escalated/deescalated at that time to the RPTD once it is determined. These patients will not be considered for evaluation of response in Phase II.

Once a RPTD is determined from the dose escalation phase I part of this trial, the dose expansion phase-II part of this trial will commence with additional patients added to the original RPTD cohort from phase I to a sample size of 22. See Figure 4-1 B. IWG-MRT response criteria will be applied at the end of cycle 6 and this will include spleen volume

measurement by MRI and bone marrow biopsy to appreciate changes in morphology, degree of reticulin/collagen fibrosis, cytogenetics and molecular markers. Patients who have obtained at least SD by IWG-MRT can remain on study receiving combination therapy in the dose extension stage of Phase II.

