1.3.3 RUXOLITINIB clinical experience

In a Phase I/II study [INC424-251] for patients with MF, a total of 154 patients were treated with increasing doses of RUXOLITINIB. 57% of patients treated sustained at least a 50% reduction in palpable splenomegaly below the left costal margin (corresponding to an approximate 35% reduction in volumetric spleen size), and were treated at doses up to 50mg BID, with activity seen at multiple dose levels from 10mg BID (n=30), 15mg BID (n=35), 25mg BID (n=47), and 50mg BID (n=5). This reduction in splenomegaly occurred regardless of presence or absence of the JAK2^{V617F} mutation and independent of the MF disease subtype (PMF, PPV-MF, or PET-MF). The responses seen regardless of the presence or absence of the JAK2^{V617F} mutation are consistent with dysregulated JAK signaling in MF patients. Within 1 month of initiating treatment, levels of pro-inflammatory cytokines and angiogenic growth factors, including CRP, IL-1ra, MIP 1 β , TNF α , and IL -6 were reduced, and patients noted

improvement in night sweats, pruritus, and abdominal pain (Verstovsek 2010). This improvement in symptoms was even seen at the lowest end of the dosing spectrum (10mg BID) even when there was not a clinically noticeable reduction in splenic size. In 34 evaluable patients, treatment with RUXOLITINIB suppressed allelic burden by 13% after 12 cycles (Verstovsek 2010).

The Modified Myelofibrosis Symptom Assessment Form (MMSAF) developed by Mesa et al, and based on an international internet-based survey of over 1000 patients with myeloproliferative diseases (Mesa 2007), was used to probe a range of constitutional symptoms that are related to splenomegaly (including impaired ability to ambulate, abdominal pain and discomfort and early satiety) and elevated cytokines (including fatigue, night sweats and pruritus). Between 45% and 94% of patients report a given symptom at baseline. After 2 or more weeks of RUXOLITINIB therapy, 28% to 61% of patients showed a reduction in individual symptom scores of at least 50% after 6 cycles of therapy when all doses were combined and assessed together.

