7.2.2 Efficacy assessments

Efficacy, beyond clinical response assessment by IWG-MRT, is an exploratory endpoint in this study.

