7.2.2.2 Disease symptom assessments/MPN-SAF

Evaluation of constitutional symptoms (weight loss $>10\%$ of the baseline value in the year preceding C1D1, unexplained fever, or excessive night sweats persisting for more than 1 month) should be performed at baseline, and the start of every cycle. The MPN-SAF validated symptom assessment tool questionnaire will be used to gauge baseline MF symptoms and changes in symptoms with treatment. See Appendix 3.

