10.5 Secondary objectives

The secondary objectives of this study are:

10.5.1 To evaluate the safety of the oral co-administration of RUXOLITINIB and PANOBINOSTAT to patients with MF

All adverse events recorded during the study will be listed and summarized. All serious adverse events will be listed by patients and tabulated by type of adverse event and initial dose level. Any other safety information will be listed and tabulated as appropriate. This includes analysis of all AE, SAE, labs, vital signs, and ECG data to include dose level and cycle.

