10.5.5 Patient-reported outcomes

Not applicable

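### Symptom response is a secondary objective and MPN-SAF is collected for it, but the analysis plan marks patient-reported outcomes as not applicable, gives no MPN-SAF analysis, and leaves the baseline open across a 28-day ruxolitinib induction

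*Combined protocol and SAP*

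**What the plan says.** The Summary lists two secondary objectives, change in spleen size and "Assess symptom response with a validated MPN tool". Section 7.2.2.2 names the tool: "The MPN-SAF validated symptom assessment tool questionnaire will be used to gauge baseline MF symptoms and changes in symptoms with treatment". Sections 7.1.2 and 7.1.2.3 collect it at screening, and the Phase 2 schedule in Appendix 2 marks it repeatedly on treatment.

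The later sections do not match:

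- Section 7.2.2: "Efficacy, beyond clinical response assessment by IWG-MRT, is an exploratory endpoint in this study".
- Section 10.5 gives one secondary objective: "To evaluate the safety of the oral co-administration of RUXOLITINIB and PANOBINOSTAT to patients with MF".
- Section 10.5.5 is headed "Patient-reported outcomes", and its whole entry is that it is not applicable.
- Section 3 has no symptom endpoint.

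Section 7.2.2.2 also asks for a separate constitutional-symptom evaluation at baseline and at the start of each cycle. Its weight criterion is a loss above 10% "of the baseline value in the year preceding C1D1, unexplained fever, or excessive night sweats persisting for more than 1 month".

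On what precedes C1D1, Section 4.1 gives every patient 28 days of single-agent ruxolitinib. Section 1.3.3 says that within a month of starting that drug patients noted "improvement in night sweats, pruritus, and abdominal pain".

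**The concern.** An objective declared at the front of the protocol is switched off in the analysis section. If the plan is followed, the questionnaires are filled in and no symptom result is due. If someone analyses them later, every choice is still open: items, threshold, time point and baseline visit.

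The baseline choice matters most. A drug expected to relieve symptoms is given between screening and C1D1, so the two visits answer different questions. Screening to end of treatment covers the whole regimen. C1D1 to end of treatment covers only the period after panobinostat is added. In an open-label, single-arm trial, choosing between them with the data in hand could decide what is reported.

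**Working it through.** **1. Does any part of the plan supply the missing analysis?**

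- Section 10.1.1 supplies a default analysis set for efficacy: patients with at least one dose of study medication.
- Section 10.8 says that secondary variables are estimated, not tested, and were not powered. It defines no symptom variable.
- Section 10.4.4 allows supportive analyses if appropriate. Section 10.5.2.5 plans none for the secondary objectives.
- Section 7.2.9.2 intends to correlate cytokines with symptom measures but does not define those measures.
- Appendix 3 lists the MPN-SAF items without a total score.

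No scoring rule, responder threshold, time point, baseline visit or missing-form rule is left. Spleen volume, the other secondary objective, has a 35% threshold, set weeks and an exact interval in Section 10.6.2.

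**2. Can the baseline be inferred from other endpoints?** No, because they differ. Spleen palpation uses C1D1 (Section 7.2.2.1). MRI/CT uses screening (Section 7.2.2.3). Transfusion dependence uses the 12 weeks before first study treatment (Section 10.6.5). Sections 5.1 and 5.2 also admit some patients without stopping ruxolitinib, so their screening score is already an on-drug score.

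**3. How much can the baseline matter?** Take hypothetical scores of 60 at screening, 36 at C1D1 and 27 at the end of Cycle 6:

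- from screening: 1 − 27/60 = 55%, a responder at a 50% threshold;
- from C1D1: 1 − 27/36 = 25%, a non-responder.

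In general, if induction alone cuts the score by a fraction r, the further cut from C1D1 needed to reach 50% from screening is 1 − 0.5/(1 − r):

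- r = 0%: 50%
- r = 20%: 37.5%
- r = 40%: 16.7%
- r = 50%: 0%

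In the last case a patient counts as a responder from screening with no further improvement on the combination. The values of r are assumptions. The documents give no mean score change for the 28-day induction.

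**4. What could be estimated?** The plan's only sizing figure for the 22 patients concerns adverse events, and it reproduces: 1 − 0.9^22 = 0.9015, against a stated 90%. It has no bearing on symptoms. If all 22 were evaluable, exact (Clopper-Pearson) 95% intervals would be:

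- 6/22 (27%): 10.7% to 50.2%
- 10/22 (45%): 24.4% to 67.8%
- 13/22 (59%): 36.4% to 79.3%

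That is wide, but usable for description.

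**The case against.** The best reply is that this is a labelling conflict over a descriptive, untested and unpowered objective in a dose-finding trial. The forms are collected, Section 7.2.2.2 says what they are for, and Section 7.2.2 calls such efficacy exploratory. DLTs, the MTD, the RPTD and the primary response do not depend on it. This stands as a limit on how serious the point is. It does not remove it, because an entry of not applicable contradicts the objective instead of leaving detail for later.

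It is also fair that the scores in the working are invented and assume a total that Appendix 3 does not define. They show the mechanism, not an expected effect. The COMFORT-1 symptom figure in Section 1.3.3 (45.9% with at least 50% improvement) came from a different form, the MFSAF, and is not a benchmark here.

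Three stronger readings are tempting and should not be drawn:

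- **That the objective cannot be answered.** The data are collected and change can be estimated once the rule is written. What is missing is the planned analysis.
- **That the fixed weight-loss window defeats the objective.** That criterion belongs to the separate constitutional-symptom check. MPN-SAF has its own item on weight loss over the last six months. Only one of the three constitutional criteria is affected, and the phrase may be meant to define the reference weight.
- **That patients with weight loss at entry cannot reach CR or PR.** Table 4-1 requires disease-related symptoms to resolve, but nothing ties it to the window in Section 7.2.2.2. Section 10.4.2.2 counts SD and better as a positive primary response in any case.

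**Conclusion.** The point holds as a contradiction plus an unstated baseline. As written, the plan produces no result for one of the two secondary objectives in the Summary. If an analysis is added later, the choice of screening or C1D1 can reverse a patient's status, as the 55% and 25% in the hypothetical example show.

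This assumes a percentage-reduction definition of response and some symptom relief during induction. Section 1.3.3 supports the relief but does not size it for this trial. The primary results are not affected.

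The weight-loss wording is a separate, minor matter of clarity.

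**What to change.** 1. Reconcile the Summary with Sections 7.2.2, 10.5 and 10.5.5, so that symptom response has one status throughout, and add a symptom endpoint to Section 3.

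2. Replace the entry in Section 10.5.5 with a descriptive analysis that:
   - names the MPN-SAF items scored and how they are combined;
   - states the denominator;
   - reports the proportion with at least a 50% reduction from screening to the end of Cycle 6, with an exact 95% interval and missing forms counted as non-response. The 50% level already appears in Sections 5.1 and 5.2 (suboptimal response to ruxolitinib) and in the COMFORT-1 result in Section 1.3.3.

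3. Beside it, report the change from C1D1 to the end of Cycle 6, with the caution that a single arm cannot separate panobinostat from a continuing ruxolitinib effect. The Phase 2 schedule appears to mark MPN-SAF at C1D1. Its columns are not reliably legible in the available text and the Phase 1 schedule cannot be read, so confirm this for both phases.

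4. Show patients who entered already on ruxolitinib separately.

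5. In Section 7.2.2.2, state the reference weight and window that apply to weight loss at on-study visits.

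The cost is plan wording and a short descriptive table from data already planned, with no added visits if the C1D1 form is confirmed. The downside is that missing questionnaires lower the reported rate, so the number missing should be shown with it.

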DS&E	Drug safety and epidemiology
DLT	Dose limiting toxicity
EC	Ethics Committee
ECG	Electrocardiogram
ECHO	Echocardiogram
ECOG	Eastern Cooperative Oncology Group
EDC	Electronic Data Capture
EPO	Erythropoietin
ET	Essential thrombocythemia
EWOC	Escalation with Overdose Control
FDA	Food and Drug Administration
FT4	Free thyroxine
G-CSF	Granulocyte colony stimulating factor
GCP	Good clinical practice
GI	Gastrointestinal
H3/4	Histone 3 or 4
HDAC	Histone deacetylase
Hgb	Hemoglobin
HIV	Human immunodeficiency virus
HL	Hodgkin's Lymphoma
HPLC	High-performance liquid chromatography
HSCT	Hematopoietic stem cell transplant
HSP90	Heat shock protein 90
Hr	Hour

IB	Investigator's brochure
i.v.	intravenous(ly)
ICF	Informed consent form
ICH	International Conference on Harmonization
IEC	Independent Ethics Committee
IL	Interleukin
INR	International normalized ratio
IRB	Institutional Review Board
IWG	International Working Guidelines
JAK1/JAK2	Janus kinase 1 or 2
LC-MS/MS	liquid chromatography-tandem mass spectrometry method
LFTs	Liver function tests
LLOQ	lower limit of quantification
LMWH	Low molecular weight heparin
LVEF	Left ventricular ejection fraction
LPFV	Last patient first visit
MAP	Master Analysis Plan documents project standards in the statistical methods which will be used within the individual clinical trial RAP documentation
MedDRA	Medical dictionary for regulatory activities
MDS	Myelodysplastic syndromes
MF	Myelofibrosis
MFSAF	Modified Myelofibrosis Symptom Assessment Form
MPD	Myeloproliferative disorder
MM	Multiple myeloma
MMSAF	Modified Myelofibrosis Symptom Assessment Form
MPL	Myeloproliferative leukemia
MPN	Myeloproliferative neoplasms
MRI	Magnetic resonance imaging
MRM	Multiple reaction monitoring
MTBE	methyl-t-butyl ether
MTD	Maximum tolerated dose
MUGA	Multi Gated Acquisition Scan
NCI	National Cancer Institute
NHL	Non-Hodgkin's Lymphoma
NIH	National Institute of Health
NYHA	New York Heart Association
o.d.	omnia die/once a day
p.o.	per os/by mouth/orally
pan	PANOBINOSTAT
PD	Progressive disease
PD	Pharmacodynamics
PET-MF	Post essential thrombocythemia-myelofibrosis
Ph	Philadelphia chromosome

PHI	Protected health information
PK	Pharmacokinetic
PK-PD	Pharmacokinetic – pharmacodynamic
PMF	Primary myelofibrosis
PPV-MF	Post polycythemia vera-myelofibrosis
PP-MF	post-polycythemia vera-myelofibrosis
PRBC	Packed red blood cells
PT	Prothrombin time
PTT	Partial thromboplastin time
PV	Polycythemia vera
q	Every
QD	Once daily
QOW	Every other week
QW	Every week
pSTAT3/5	Phosphorylated signal-transducer and activator of transcription 3 or 5
RA - need subscript A	Accumulation ratio
RAP	The Report and Analysis Plan (RAP) is a regulatory document which provides evidence of preplanned analyses
RBC/HPF	Red blood cells/high power field
REB	Research Ethics Board
RPTD	Recommended Phase 2 Dose
rux	RUXOLITINIB
SAE	Serious Adverse Event
SD	Standard deviation
SEC	Safety event categories
STAT	Signal transducers and activators of transcription
T1/2	Half life
Tmax	Maximum plasma concentration time
TEAE	Treatment emergent adverse event
TIW	Three times a week
TK	Tyrosine kinase
tlast	time zero to the last measurable concentration sampling time
TNF	Tumor necrosis factor
TSH	Thyroid stimulating hormone
ULN	Upper limit of normal
WBC	White blood cell count
WBC/HPF	White blood cells/high power field
WHO	World Health Organization

Glossary of terms

Assessment	A procedure used to generate data required by the study
Control drug	A study treatment used as a comparator to reduce assessment bias, preserve blinding of investigational drug, assess internal study validity, and/or evaluate comparative effects of the investigational drug
Cycles	Number and timing or recommended repetitions of therapy are usually expressed as number of days (eg: q28 days)
Enrollment	Point/time of patient entry into the study; the point at which informed consent must be obtained (i.e. prior to starting any of the procedures described in the protocol)
Investigational drug	The study treatment whose properties are being tested in the study; this definition is consistent with US CFR 21 Section 312.3 and is synonymous with "investigational new drug."
Investigational treatment	Drug whose properties are being tested in the study as well as their associated placebo and active treatment controls (when applicable). This also includes approved drugs used outside of their indication/approved dosage, or that are tested in a fixed combination. Investigational treatment generally does not include other study treatments administered as concomitant background therapy required or allowed by the protocol when used in within approved indication/dosage
Medication number	A unique identifier on the label of each study treatment package which is linked to one of the treatment groups of a study
Other study treatment	Any drug administered to the patient as part of the required study procedures that was not included in the investigational treatment
Patient Number (Patient No.)	A unique identifying number assigned to each patient who enrolls in the study
Period	A subdivision of the study timeline; divides stages into smaller functional segments such as screening, baseline, titration, washout, etc.
Premature patient withdrawal	Point/time when the patient exits from the study prior to the planned completion of all study treatment administration and/or assessments; at this time all study treatment administration is discontinued and no further assessments are planned, unless the patient will be followed for progression and/or survival
Stage related to study timeline	A major subdivision of the study timeline; begins and ends with major study milestones such as enrollment, randomization, completion of treatment, etc.
Stop study participation	Point/time at which the patient came in for a final evaluation visit or when study treatment was discontinued whichever is later
Study treatment	Includes any drug or combination of drugs in any study arm administered to the patient (subject) as part of the required study procedures. =
Study treatment discontinuation	Point/time when patient permanently stops taking study treatment for any reason; may or may not also be the point/time of premature patient withdrawal
Variable	Identifier used in the data analysis; derived directly or indirectly from data collected using specified assessments at specified timepoints

1 Background

